2.0 OBJECTIVES AND SCIENTIFIC AIMS

- 2.1 Demonstrate in a pilot study (n=30) that [18F]-FACBC has equal or better brain tumor imaging characteristics compared to [11C]-methionine.

- 2.2 Determine the biodistribution and clearance of 3-[18F]-FACBC in different tissues/organs of the body using PET, and calculate body and critical organ radioactivity exposure (dosimetry).
- 2.3 The results of this study will be used to support the submission of an investigational new drug (IND) application to the Food and Drug Agency (FDA).
- 2.4 Look for potential correlations between subsequent MR and PET scan results obtained from those patients enrolled to 03-028 and the patients' subsequent medical treatment, progression of the tumor and survival.

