4.0 STUDY DESIGN

- 4.1 The first set of 20 patients will consent to two PET studies. One study will involve the i.v. administration of a fluorine-18 labeled amino acid analogue, 3-fluoro-aminocyclobutane carboxylic acid (3-[18F]-FACBC) with sequential brain and body PET imaging. The second study will involve i.v. administration of [11C-methyl]-L-methionine for a head imaging study only. An additional set of 10 patients will consent to one type of PET study which will involve administration of [18F]-FACBC only for one brain scan and one body scan.
- 4.2 ~~All~~The first set of 20 patients will first undergo a [11C-methyl]-L-methionine PET study. Whenever possible, approximately two hours later, the same patient will undergo the [18F]-FACBC PET study.
- 4.3 For the first 20 patients, we will attempt to complete both studies on the same day; if this is not possible, the two PET studies will be completed within 1 week of each other.

- 4.4 The 3-[18F]-FACBC and [11C-methyl]-L-methionine PET images will be digitally registered to each other and to corresponding contrast enhanced and FLAIR MR images (from the most recent MR study obtained as part of the patient's standard medical care). Region of interest (ROI) measurements of 3-[18F]-FACBC and [11C-methyl]-L-methionine activity in tumor and remote brain tissue will be obtained from the two data sets and paired comparisons will be performed.
- 4.5 The study will also provide data to determine body and critical organ radioactivity exposure (dosimetry) following 3-[18F]-FACBC administration. These calculations will be based on the biodistribution and clearance of radioactivity from the tissues and organs of the body as determined by sequential PET imaging.
- 4.6 Look for potential correlations between the MR and PET scan results obtained from those patients enrolled to 03-028 and the patients' past medical treatment, as well as the patients' subsequent medical treatment, progression of the tumor and survival. _

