9.0 TREATMENT/INTERVENTION PLAN

- 9.1 All subjects will be pre-registered at MSKCC and will have signed the consent form prior to participation in this study.
- 9.2 The morning of the PET imaging studies, all patients will be asked to avoid high protein foods (meat, fish, poultry, cheese, eggs, beans and nuts) and to record the types and servings of the foods they eat. Some patients may also be asked to avoid high protein foods the day prior to imaging. These same patients will also be asked to refrain from eating lunch on the day of the study to reduce muscle uptake of the FACBC. All patients will also be urged to drink several glasses of water to attain good hydration and urine output. Patients will be placed comfortably on the couch and positioned in the GE Advance PET scanner. The first 20 patients will first receive 185 MBq (5 mCi) of [11C-methyl]-L-methionine by i.v. infusion over approximately 1 minute. Whenever possible, approximately 1.5 to 2 hours later, the same patient will receive 370 MBq (10 mCi) [18F]-FACBC by i.v. infusion over approximately 1 minute. In cases where both studies cannot be obtained on the same day, they will be obtained within one week of each other.
- 9.3 For the first 20 patients, the [11C-methyl]-L-methionine study will involve a 45-minute emission dynamic scan of the head. Previous studies have shown that [11C-methyl]-L-methionine accumulation in tumor and brain tends to reach a plateau value within 15-30 minutes following administration. The [18F]-FACBC study will involve a 45-minute emission dynamic scan of the head to obtain kinetic information on tumor uptake for modeling. After the initial dynamic scan, the patient will void completely; the volume of urine will be recorded and a urine sample will be assayed for urine radioactivity. Up to three [18F]-FACBC body scans will be performed following the completion of the dynamic scan to obtain data for calculating body and organ specific dosimetry. The last 10 patients will undergo a [18F]-FACBC 45-minute emission dynamic scan of the head followed by one body scan.

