- 10.4 The second level of analysis will be quantitative. Volumes of interest (VOI) will be drawn on the lesions that are positive on the 3-[18F]-FACBC scan; VOI's on remote normal white and gray-matter regions of the brain will also be drawn. The mean of the voxel values within each VOI will be determined for each of the dynamic frames of the 3-[18F]-FACBC study. Profiles will be generated in units of: 1) standard uptake value [$SUV = (\% \text{ dose/g}) * \text{body weight}$] versus time, and 2) the brain tumor-to-gray or white matter ratio versus time. These curves will be evaluated to determine a single, near "optimal" tumor imaging time, for each of the patients. The criteria used in making this assessment will be target to background contrast, robustness (i.e. time insensitivity) and image noise level. The SUV and ratio values at this "optimal" time point will then be compared to similar SUV and lesion to background values determined for the corresponding location within the [11C]-methionine scan..
- 10.5 Radiolabeled metabolites of 3-[18F]-FACBC, if any, in plasma and urine will be assayed by HPLC and % parent compound vs. time profiles will be constructed for plasma and urine, and compared to the tissue radioactivity concentration vs. time profiles calculated above and used for calculating the kinetic parameters.
- 10.6 The absorbed tissue radioactivity dose estimates for 3-[18F]-FACBC will be calculated in the standard manner. Attenuation corrected PET images provide information for the tumor and organ activities directly in units of activity per cubic centimeter. Regions of interest will be drawn within identified normal organs e.g. brain, lung, liver, bladder etc. This data will be plotted versus time post injection and used for determining organ residence times. These organ residence times will be entered into MIRDOSE for determination of the organ dosimetry. MIRDOSE is a personal computer software package for internal dose assessment from tracers used in nuclear medicine [13]. This program calculates the radiation dose to each organ from the activity residing within that organ, as well as the contribution of the penetrating photon emissions from other body organs accumulating significant levels of radioactivity, according to the methodology laid out by the Medical Internal Radiation Dose (MIRD) Committee [14] (MIRD PRIMER 1988).

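### Section 10.4 picks the FACBC read time patient by patient, partly on contrast, and describes no such choice for methionine, which tilts the paired ratio comparison toward FACBC

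*Combined protocol and SAP*

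**What the plan says.** - Objective 2.1 is to show that FACBC "has equal or better brain tumor imaging characteristics compared to [11C]-methionine". Section 4.4 says that for ROI measurements in tumour and remote brain "paired comparisons will be performed". Only the first 20 patients receive both tracers (4.1: "The first set of 20 patients will consent to two PET studies"), so there are at most 20 pairs.
- Section 10.4 describes the FACBC measurement: "The mean of the voxel values within each VOI will be determined for each of the dynamic frames of the 3-[18F]-FACBC study". SUV and tumour-to-brain ratio are plotted against time, and one near-optimal "tumor imaging time, for each of the patients. The criteria used in making this assessment will be target to background contrast" is read off, with robustness (insensitivity to time) and image noise completing the list. The three criteria are neither ranked nor weighted.
- The FACBC SUV and ratio at that time are then set against similar values at the corresponding location in the methionine scan. No methionine curve, frame, read time or time search is described.
- Section 9.3 gives methionine a dynamic acquisition of the same length ("the [11C-methyl]-L-methionine study will involve a 45-minute emission dynamic scan of the head") and says that uptake tends to plateau within 15-30 minutes.
- Section 14 gives no test, significance level, margin or fixed read time for the tracer comparison.

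**The concern.** A reading chosen partly because its contrast is high will, on average, lie above that patient's typical contrast. Some of the excess is frame noise, and some is the patient's own kinetics. If the comparator reading is not chosen in the same way, the paired difference in ratio carries this excess in one direction only. More patients would not remove it. The results are meant to support an IND application (2.3), and a modest FACBC advantage in the ratio could not be separated from the way the FACBC time was chosen. A time tuned to each patient also says little about performance in routine imaging, where the scan time is set in advance.

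**Working it through.** **The plan's own figure.** The only precision statement is in 14.2 and concerns mean organ values, not the tracer comparison. With CoV 24.4% on the log scale:
- n = 10: exp(1.96 × 0.244/√10) − 1 = 16.3%
- n = 20: exp(1.96 × 0.244/√20) − 1 = 11.3%

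These reproduce the stated 16% and 11%. They give neither frame noise nor a paired SD for tumour ratios.

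**Inputs from the documents.** 20 pairs (4.1); 45-minute dynamic scans for both tracers and a methionine plateau within 15-30 minutes (9.3); log scale (14.2).

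**Inputs assumed, because the documents do not give them.** Six 5-minute frames over 15-45 minutes; independent frame noise with SD 2%, 5% or 10% of the ratio; paired log SD 0.10 or 0.25; methionine read as the mean of its six frames; true ratios identical for the two tracers.

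**Single best frame.** The expected maximum of six independent standard normal values is 1.267, so the inflation is about 1.267 × frame SD:
- 2%: 2.5%
- 5%: 6.3%
- 10%: 12.7%

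This rule ignores robustness and image noise. It serves as an upper bound under these assumptions, not as a model of 10.4.

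**Best 15-minute average.** This allows for robustness by taking the highest of the four running three-frame means. Results are by simulation. The false-result columns add a one-sided 2.5% paired t-test on logs, which the plan does not specify.

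| Frame noise SD | Inflation of FACBC ratio | False FACBC-better result, paired SD 0.25 | Same, paired SD 0.10 |
|---|---|---|---|
| 2% | about 0.9% | about 4% | about 6% |
| 5% | about 2.2% | about 5% | about 13% |
| 10% | about 4.3% | about 10% | about 33% |

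**Sensitivity.** With 5 to 9 frames, noise 3-10%, a per-tracer log SD of 0.10-0.172 and methionine read at one fixed frame, the three-frame rule gives an inflation of 1.0-6.6%. Adding patient-specific slopes (log SD 0.05-0.10, nine frames, 5% noise, per-tracer SD 0.10) gives 4.5-7.1%. A time chosen on stability alone, without contrast, gives 0%.

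**Check of remedies.**
- The same rule for both tracers, or windows fixed in advance: bias about 0%. With the same rule, the false-result rate stays close to the nominal 2.5%.
- A FACBC window picked from the pooled curve of the same 20 patients: about 0.2-0.9% bias remains, because the window is still chosen on the outcome.

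**The case against.** The strongest case on the other side has four parts.

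1. **Contrast is one of three criteria.** Robustness and image noise both work against choosing an isolated noisy peak. This stands. A reader might infer that 10.4 takes the highest-contrast frame, with an inflation of 6-13% and a false-result rate of 68-98% (frame noise 5-10%, paired SD 0.10). The text does not describe that rule. The bias shrinks under the softer reading, but it remains as long as contrast carries any weight.
2. **The plan is silent on the methionine time; it does not rule a search out.** This also stands. A reader might infer a deliberately one-sided rule, and the documents do not say that. If similar values were meant to include the same search, the bias would vanish. But frame-by-frame extraction is stated for FACBC only, so following 10.4 as written leads to the asymmetry. The methionine plateau is a reason to fix a methionine window. It does not justify comparing that window with a FACBC time searched in each patient.
3. **This is a pilot with no planned test.** Correct: the 2.5% level is an assumption of this review. The direct harm is a biased descriptive difference, and the false-result rates only show what would follow if a test were applied.
4. **Scope.** A reader might infer that the time rule alone could decide objective 2.1. That goes too far. The visual scoring in 10.3 does not use this time, and SUV is affected only indirectly.

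**Conclusion.** The point holds for the tumour-to-brain ratio comparison in 10.4. The direction follows from the text: contrast helps select the FACBC reading and is then compared with a methionine reading for which no selection is described. The size does not follow from the text, because frame count, frame noise and paired SD are not given.

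Under the stated assumptions, a best 15-minute-average rule inflates the FACBC ratio by about 1-4%. If a one-sided 2.5% paired test were used, equal tracers would yield a false FACBC-better result in about 4-10% of trials at a paired log SD of 0.25, and about 6-33% at 0.10. Patient-specific kinetics could raise these figures, and greater weight on stability would lower them. The single-best-frame figures (about 2.5-13%) are only an upper bound within the same assumptions. Severity: should-fix.

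**What to change.** Amend 10.4 as follows.
- Extract VOI curves for both tracers from their 45-minute dynamic scans.
- Make the paired comparison in one of two ways. Either use one window per tracer, the same for all patients and fixed before the paired data are examined (for methionine, the post-plateau period indicated in 9.3), or apply the identical written time-selection rule to both tracers.
- Do not choose the FACBC window from the pooled curve of the same 20 patients.
- Report the per-patient FACBC optimal time as a description only, alongside the full ratio-time curves for both tracers.

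The cost is a wording change and some additional VOI extraction from scans already in the plan, with no further patients, injections or scans. The FACBC ratio will come out slightly less favourable.

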- 9.4 A venous catheter will be placed in a superficial hand or arm vein for administration of the radiopharmaceuticals. A second venous catheter will be placed in the opposite hand or arm for "warmed arterialized" venous blood sampling. For the first 20 patients, a blood sample will be obtained just prior to the injection of [11C-methyl]-L-methionine and [18F]-FACBC to measure plasma amino acid concentration at the time of each study. Sequential blood samples will be obtained following [18F]-FACBC infusion and assayed for whole blood and plasma radioactivity, to check for radiolabeled metabolites by HPLC, and to measure plasma amino acid concentration at the time of the study. All catheters will be removed at the end of the day.

- 9.5 After the [18F]-FACBC head scan and ~10-15 min break period, patients will be placed comfortably on the couch and positioned in the GE Advance PET scanner for sequential body imaging. The total time in the scanner for each imaging sequence will be up to 45 minutes. For the first 20 patients, this sequence of scans will be repeated a maximum of three times over a four hour post injection period (approximately two 18-F half lives). The first body scan sequence will commence ~60 min after [18F]-FACBC injection. The second and third sequences will commence at ~2 and ~3 hours post-injection of [18F]-FACBC, respectively, with a break between scans. During the intervals between scans, the patient will come out of the scanner, exercise and will be asked to void completely. To assist correct re-alignment in the scanner for repeat scans, the patient's skin will be "marked" to identify the plane defined by the PET laser during the first scan set. On the second and third scans, the technologist will position each patient field of view so as to align the laser with the skin markings.
- 9.6 Venous blood will be sampled before the methionine and FACBC scans to measure plasma amino acid concentrations. Blood samples (1/2 teaspoon per sample) will be drawn during the FACBC scans to measure the radioactivity level in your blood. Total blood sampled for the two PET studies will be less than 6 tablespoons (less than 90 ml). Whole blood and plasma will be assayed for radioactivity and for radiolabeled metabolites by HPLC.

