The plasma and urine radioactivity concentration data (nCi/cc) will be plotted vs. time after injection. The integral of activity-time curve will be calculated from zero to infinity and multiplied by the equilibrium dose constant for 18F to obtain the absorbed dose to blood. The dose to the bladder wall will be determined using the dynamic bladder model of Cloutier et al. [15], as implemented in MIRDOSE using measured clearance data from urine samples.

The dose estimates described above incorporate estimates of the biological clearance of the tracer. Companion calculations will also be performed using the assumption of no biological clearance, i.e. only physical decay from the organ maximum. This is a

conservative “worst case” scenario and does not depend on the accuracy of the organ clearance fits.

- 10.7 Look for potential correlations between the MR and PET scan results obtained from those patients enrolled to 03-028 and the patients’ past medical treatment, as well as the patients’ subsequent medical treatment, progression of the tumor and survival.

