11.0 TOXICITIES/SIDE EFFECTS

- 11.1 PET Scanning. Potential risks to the patient are small, and present more of an inconvenience (multiple scans on consecutive days). The GE Advance tomograph has a large bore (92.7 cm in diameter) to accommodate the whole body and the environment is much less confining than the head cage of the General Electric Signa 1.5 Tesla MR tomograph. For the first 20 patients, the length of time in the PET scanner will be ~45 min for the [11C-methionine head scan; for the [18F]-FACBC scan, an initial scanning period of the head will be ~45 min, followed by ~45 min for each of the up to three subsequent body scan periods (maximum total time in the scanner for the [18F]-FACBC imaging series will be ~180 minutes). The last 10 patients will be scanned for a maximum of ~90 minutes (an initial [18F]-FACBC scanning period of the head will be ~45 min, followed by a ~45 min body scan). This is long and could produce some discomfort because movement and changes of position will be discouraged. However, there will be substantial breaks between each of the [18F]-FACBC imaging sequences where the patient will come out of the scanner. Many studies on patients have been performed for this length of time and longer.
- 11.2 Radiation Exposure. The radiation exposure from diagnostic 3-[18F]-FACBC or [11C-methyl]-L-methionine PET studies is expected to be within acceptable limits as established by FDA Guidelines (Code of Federal Regulations, Section 361.1). Dosimetry estimates of [11C-methyl]-L-methionine to critical organs have been reported [16 and Appendix B]. Preliminary measurements of 3-[18F]-FACBC dosimetry performed Emory have been reported [11 and Appendix B] and will be extended by results obtained in this study.
- 11.3 The dosimetry estimates in Appendices B have led us to select a conservative 185 MBq (5 mCi) dose of [11C-methyl]-L-methionine and a 370 MBq (10 mCi) dose of 3-[18F]-FACBC for this study. This will maintain the radioactivity exposure to all normal tissue (including whole body, blood forming organs and gonads) well below the annual radiation dose limit of 5 cSv established by the FDA (Code of Federal Regulations, Section 361.1) (see Appendix B). In the event that our measurements and dosimetry estimates for 3-[18F]-FACBC exceed the annual radiation dose limit of 5 cSv established by the FDA, we will reduce the administered dose of 3-[18F]-FACBC to insure that the annual radiation dose limit of 5 cSv is not exceeded.

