14.0 BIOSTATISTICS

- 14.1 This is a pilot study involving only ~~20~~ 30 patients initially. Basic measurements (biodistribution, clearance, radioactivity exposure) will be summarized as means, ranges and standard deviations.
- 14.2 Published data in humans and our own prior laboratory experience indicate that statistical analyses of measurements of the type we propose to study would benefit from first applying a logarithmic transformation. For example, cumulated activities per unit of administered activity in Table 3 of [17] had nearly constant coefficients of variation (CoV) within subgroups of organs: 24.7% average CoV for brain, heart, kidneys and liver and 11.9% average CoV for lungs, pancreas and spleen. (Note that we corrected the published calculations of standard deviations to the unbiased estimate using divisor = n-1.) Our own preliminary animal data had an average CoV of 24.4%. This suggests that mean organ values could be estimated with 95% confidence to within +/- 16% from a sample of size 10, and within +/- 11% from a sample of size 20.
- 14.3 Randomization of the sequence of studies will not be performed because of our objective to perform both studies on the same day; the [11C-methyl]-L-methionine study must be performed first because 11-C has the shorter physical half-life (20 minutes vs. 110 min for 18-F). A 3 or more hour interval will separate the [11C-methyl]-L-methionine and 3-[18F]-FACBC studies to allow for near complete 11-C decay.
- 14.4 Data may be compared to FDG scans, when available.

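### Section 10.6 takes the absorbed dose to blood from a plasma curve although whole blood is assayed; the size and direction of the resulting error cannot be known from the documents

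*Combined protocol and SAP*

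**What the plan says.** The blood-dose calculation is in the unnumbered paragraph that follows the MIRDOSE description in section 10.6. It opens with "The plasma and urine radioactivity concentration data (nCi/cc) will be plotted vs. time after injection". The next sentence integrates an activity-time curve from zero to infinity, without saying which one, and the integral is "multiplied by the equilibrium dose constant for 18F to obtain the absorbed dose to blood". The same paragraph then uses urine clearance data for the bladder wall.

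Section 9 describes what is measured. Under 9.4, "Sequential blood samples will be obtained following [18F]-FACBC infusion and assayed for whole blood and plasma radioactivity". Section 9.6 repeats it: "Whole blood and plasma will be assayed for radioactivity and for radiolabeled metabolites by HPLC". Section 10 does not mention the whole-blood result again. Section 10.5 uses plasma and urine for the parent-compound profiles and the kinetic parameters. The documents give no haematocrit, no red-cell partition for FACBC and no plasma-to-blood conversion.

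**The concern.** Blood is plasma plus red cells. A plasma concentration stands in for a whole-blood concentration only when red cells carry the tracer at the same concentration as plasma. If they carry less, the plasma curve lies above the whole-blood curve and the blood dose is overstated. If they carry more, it is understated. The protocol offers no evidence on which applies to FACBC, yet it already obtains the measurement that would make the question unnecessary.

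What is at stake is one reported dosimetry figure in a study whose results are meant to support an IND application (section 2.3). The error comes from measuring the wrong compartment, so enrolling more patients would not shrink it.

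**Working it through.** The plan states no blood dose and no plasma-to-blood ratio, so there is no figure of its own to reproduce first.

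**Inputs from the documents.** The curves named are plasma and urine (10.6). The dose is the integral times the 18F equilibrium dose constant (10.6). Whole blood and plasma are both assayed (9.4, 9.6). The physical half-life of 18F is 110 minutes (14.3).

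**Assumed inputs.** Haematocrit H = 0.35 to 0.48. Red-cell-to-plasma concentration ratio r, constant over time, varied from 0 to 1.5.

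**Step 1: which curve.** Of the two curves plotted, urine is not a blood compartment. Plasma is the only candidate left.

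**Step 2: ratio of the two doses.** Whole-blood concentration = plasma × (1 − H) + red cells × H = plasma × (1 − H + H·r). The same dose constant multiplies either integral and cancels, so

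plasma-based dose / whole-blood dose = 1 / (1 − H + H·r).

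| r | H = 0.35 | H = 0.48 |
|---|---|---|
| 0 | 1/0.65 = 1.54 | 1/0.52 = 1.92 |
| 0.5 | 1/0.825 = 1.21 | 1/0.76 = 1.32 |
| 1 | 1.00 | 1.00 |
| 1.5 | 1/1.175 = 0.85 | 1/1.24 = 0.81 |

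**Step 3: gradual entry into red cells.** The r = 0 row requires that no tracer enters red cells at any time up to infinity. As an illustration, assume instead that plasma falls by physical decay only and that r rises exponentially from 0 to 1 with half-time T minutes. The ratio of integrals becomes 1 / (1 − H·T/(T + 110)).

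- T = 30: T/(T + 110) = 0.214, ratio 1.08 to 1.11.
- T = 60: 0.353, ratio 1.14 to 1.20.
- T = 120: 0.522, ratio 1.22 to 1.33.

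**Step 4: where the blood figure goes.** Section 10.6 takes organ doses from image-derived residence times entered into MIRDOSE, and the bladder-wall dose from urine clearance in the dynamic bladder model. Neither is said to use the plasma integral.

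**The case against.** The strongest reply is that this is compressed drafting rather than a chosen analysis. The sentence on integration does not name its curve. Read literally, the sentence before it would put urine into the blood dose as well, which nobody intends. Section 9.6 says that samples are drawn to measure radioactivity in the blood, so the team may mean to use whole blood. Both assays exist, so the dose could be recalculated at any time. That the wording is loose, and that nothing is lost for good, stands. It does not remove the point: anyone following the text as written would integrate plasma and label the result blood.

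Two stronger readings are tempting, and the documents support neither.

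- *The blood dose is overstated by 1.5 to 1.9 times.* This is the r = 0 ceiling under an assumed haematocrit. With red-cell entry the ratio falls towards 1, and with r above 1 the sign reverses. The documents do not exclude any of these cases.
- *The study's dosimetry, or its check against the 5 cSv limit, is compromised.* Objective 2.2 speaks of body and critical organ exposure determined by PET and does not name blood. Section 11.3 refers to all normal tissue and lists "including whole body, blood forming organs and gonads) well below the annual radiation dose limit of 5 cSv established by the FDA"; circulating blood is not listed. The dose-reduction provision ("In the event that our measurements and dosimetry estimates for 3-[18F]-FACBC exceed the annual radiation dose limit of 5 cSv established by the FDA") concerns the FACBC dosimetry estimates in general, and nothing shows that the blood figure would decide it. If the error were an overstatement, it would also be conservative against the limit, although that cannot be relied on while the direction is unknown.

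**Conclusion.** The mismatch is real and narrow. As written, section 10.6 yields a plasma dose under the name of a blood dose, while the whole-blood measurement from the same samples goes unused. Neither size nor direction follows from the documents. Under an assumed haematocrit of 0.35 to 0.48, the ratio runs from at most 1.92 with no red-cell uptake, through exactly 1 at equal concentrations, to as low as 0.81 if red cells hold one and a half times the plasma concentration. That last ratio is itself only an example and not a floor. The effect is confined to the reported blood dose. It is worth correcting because the correct input is already available, not because a large bias has been shown.

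**What to change.** In section 10.6, state that the whole-blood activity-time curve is the one integrated and multiplied by the 18F dose constant to give the absorbed dose to blood. Keep the plasma curve for the parent-compound and kinetic analyses in 10.5, and say that the urine data serve the bladder model only. If plasma is to be kept for the blood dose, the section would need to state and justify a plasma-to-blood conversion, which is more work than using the measured whole blood.

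The cost is one sentence. Sections 9.4 and 9.6 already provide the assays, so no sample, scan or procedure is added and no other dose calculation changes.

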- 9.7 The volume of urine voided between scans will be recorded and a urine sample will be assayed for urine radioactivity and radiolabeled metabolites by HPLC. This frequent urination will reduce bladder exposure and provide a brief "relaxation" period between sequential sets of scans, and will facilitate individual patient acceptance and compliance during the study.

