10.0 EVALUATION DURING TREATMENT/INTERVENTION

- 10.1 Reconstructed images will be obtained from the PET data; corrections will be made for randoms, scatter, dead-time, detector inhomogeneity and attenuation. Image data will be calibrated to nCi/cc and decay corrected to the time of injection. Comparisons will be made with the most recent MRI study obtained as part of the patient's standard radiographic assessment. The PET and MRI scans will be digitally co-registered using established methods at MSKCC to facilitate this comparison.
- 10.2 The registered image sets will be displayed simultaneously, facilitating the identification of the correspondence between the lesion(s) in each modality. Volumes of interest created on one modality will be applied to the other modalities, thus enabling direct quantitative comparisons.
- 10.3 Two levels of image analysis will be performed. One level will involve two Nuclear Medicine physicians (or one Nuclear Medicine physician and one Neurologist) who will independently view the full set of registered images. The analysis will involve assessment for the presence or absence of disease using a five point visual scoring system. These assessments will be blinded to the clinical and pathologic results pertaining to the patient, although all imaging studies (including MRI) will be available

(which is standard clinical practice). We chose a five point scale rating disease from 0-4 in terms of probability for the presence of disease (0=no evidence of tumor, 1=probably no evidence of tumor, 2=equivocal for the presence of tumor, 3=probably tumor present, 4=definitely tumor present).

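### For the bladder, the no-clearance worst case in section 10.6 is not a reliable upper bound when voiding is less frequent than in the study

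*Combined protocol and SAP*

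**What the plan says.** Section 10.6 derives organ residence times from regions of interest: "Regions of interest will be drawn within identified normal organs e.g. brain, lung, liver, bladder etc". Bladder-wall dose has its own method, a dynamic bladder model "as implemented in MIRDOSE using measured clearance data from urine samples". No voiding interval is given for that model.

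The section then continues: "The dose estimates described above incorporate estimates of the biological clearance of the tracer". It adds the no-clearance version: "Companion calculations will also be performed using the assumption of no biological clearance, i.e. only physical decay from the organ maximum". This is described as a conservative worst case that does not rely on the clearance fits. No organ is excepted.

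Four other provisions bear on the bladder maximum:

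- Section 10.1: "Image data will be calibrated to nCi/cc and decay corrected to the time of injection".
- Section 9.3: "After the initial dynamic scan, the patient will void completely".
- Section 9.5: "The first body scan sequence will commence ~60 min after [18F]-FACBC injection". The second and third body scans start at about 2 and 3 h, with complete voids requested between scans.
- Section 9.7, on voiding between scans: "This frequent urination will reduce bladder exposure".

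The last 10 patients have one head scan and one body scan, so they have fewer scheduled voids.

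**The concern.** Setting biological clearance to zero bounds the dose to an organ that takes up tracer and then loses it. The bladder works the other way: what the rest of the body clears is what fills it. Its observed peak is also cut short by emptying at roughly hourly intervals, and the first bladder image comes after the first void. Letting that reduced peak decay physically does not account for urine that would collect over a longer interval.

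Hypothesis 4 in the Summary is that 370 MBq is safe and within FDA guidelines, and aim 2.3 is to support an IND. A bladder figure carrying a worst-case label could be read in that setting as covering ordinary clinical use. Nothing in the plan imposes near-hourly voiding there.

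**Working it through.** The documents give no bladder dose, urinary fraction or residence time, so there is no stated figure to reproduce. What can be checked is the ratio of the companion to cumulated bladder activity. The excreted fraction cancels from this ratio.

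**Inputs**

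- 18F half-life 110 min (section 14.3), so λp = ln 2/110 = 0.00630 per min and 1/λp = 158.7 min.
- Body-scan windows 60–105, 120–165 and 180–225 min (section 9.5, up to 45 min each).
- Assumed: complete voids at 45, 110, 170 and 225 min, then every 4 h, for the first 20 patients.
- Assumed: single-exponential excretion with rate λb and half-time 0.5 to 24 h. The documents give no value for FACBC.

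**Formulas (per unit of excreted fraction)**

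- Bladder activity at time t, after a void at a and before the next at b: [exp(−λb·a) − exp(−λb·t)]·exp(−λp·t).
- Cumulated activity: the integral of this from a to b, summed over intervals.
- Companion: (largest bladder content on a body scan, decay-corrected to injection as in 10.1)/λp.
- Ratio: companion/cumulated activity. Below 1, the companion is not a bound.

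**Worked case, half-time 1 h (λb = ln 2/60)**

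- The imaged maximum falls at the end of the first body scan: exp(−45λb) − exp(−105λb) = 0.5946 − 0.2973 = 0.2973. The companion is 0.2973 × 158.7 = 47.18 min.
- Regular 4 h voiding, first interval: (1 − 0.2204) × 158.7 − (1 − 0.0138)/0.01785 = 68.48 min. Each later interval is 0.0138 times the one before, so the total is 68.48/(1 − 0.0138) = 69.44 min. Ratio 47.18/69.44 = 0.68.
- First 20's schedule, same integral: 18.56 min. Ratio 47.18/18.56 = 2.54.

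**Ratio by excretion half-time**

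| Half-time (h) | Regular 4 h from injection | Head-scan void, then 4 h | Regular 2 h | First 20's schedule |
|---|---|---|---|---|
| 0.5 | 0.47 | 1.10 | 0.80 | 1.93 |
| 1 | 0.68 | 1.20 | 1.20 | 2.54 |
| 2 | 0.74 | 1.11 | 1.32 | 2.36 |
| 4 | 0.73 | 0.99 | 1.29 | 1.99 |
| 10 | 0.70 | 0.90 | 1.22 | 1.67 |
| 24 | 0.68 | 0.85 | 1.18 | 1.53 |

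The regular interval beyond which the companion stops being a bound is 1.6 to 2.7 h.

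**Sensitivity**

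- Maximum taken from the true peak during the study, including urine voided before imaging: 0.73 to 1.14 at regular 4 h voiding, above 1 only at a half-time of 0.5 h. The break-even interval is 2.7 to 5.2 h.
- Study voids at 60, 120, 180 and 225 min, imaged maximum: 0.29 to 0.54 at regular 4 h voiding, and 0.97 to 1.59 on the first 20's own schedule.
- Last 10 patients: 0.85 to 1.20 if the head-scan void is their only void before a 4 h gap, and 1.09 to 1.91 if they also void after the body scan.

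**The case against.** **Reading.** The bladder wall has a dedicated model, and the companion's wording suits the imaged source organs. It can be argued that the companion was never meant for the bladder. This partly stands: the application is not explicit. But the bladder is listed among the regions of interest, its wall dose is the estimate immediately before the companion, and no exception is written.

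**Purpose.** The companion is meant to remove dependence on clearance fits, and the plan does not say that it covers other voiding schedules or which bladder figure will go into the IND. That is fair. It limits the point to what the label can be taken to mean.

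**Comparator.** Regular 4 h voiding from injection drops even the void after the head scan. With that void kept, the shortfall at 4 h is at most 15%, and the companion holds at 3 h (1.03 to 1.41). This stands under the base void times. With the later void times, the 3 h and 4 h ratios fall below 1, so the answer depends on timings that the plan does not fix.

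**Stronger inferences.** A reader might conclude that the companion is always too low, or that it already fails for the participants. The calculations do not support this. It bounds the first 20's schedule in nearly all cases and regular 2 h voiding at most half-times under the base timings. The last 10 fall short only if they do not void after the body scan and the half-time is 4 h or more.

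**Conclusion.** The point holds in a limited form. If the section 10.6 companion is applied to the bladder, it is not a reliable upper bound at voiding intervals longer than the study's. Using the imaged, decay-corrected maximum, it covers 47% to 74% of cumulated activity at regular 4 h voiding and 85% to 120% if the head-scan void is kept first.

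This rests on assumed single-exponential excretion, assumed void times and complete emptying. The ratios are cumulated activity, not wall dose; a fuller bladder may lower wall dose per unit activity, and no volumes are given. If urinary excretion is small, the absolute effect is small too.

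A reader might also infer that 370 MBq would breach 5 cSv. The documents do not support that: they give no urinary fraction or absolute bladder dose from which it could be shown. Nor is the primary bladder estimate at fault, since it uses measured urine data in a suitable model. Priority is therefore minor: a cheap improvement to one safety figure.

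**What to change.** In section 10.6:

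- Exclude the bladder from the no-clearance companion, and leave the companion unchanged for other organs.
- Run the planned dynamic bladder model on the measured urine data at the study schedule, 2 h and about 4 h voiding.
- Report bladder-wall dose with the voiding interval stated for each run.
- Use the longest interval as the bladder worst case for hypothesis 4 and the IND.

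In section 11.3, apply the dose-limit check to the voiding schedule participants actually follow, including the last 10.

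The cost is one or two sentences and a few extra runs of software already in the plan. Urine volume and activity are already being collected, so no new data or change to voiding instructions is needed. The downside is a less favourable bladder figure.
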